ELISA	Enzyme Linked Immunosorbent Assay
EP	European Pharmacopoeia
EU	European Union
GCP	Good Clinical Practice
Gamma-GT	Gamma glutamyl transferase
GPI	Glycosylphosphatidylinositol
GMP	Good Manufacturing Process
FSH	Follicle Stimulating Hormone
HPP	Hypophosphatasia
IB	Investigator Brochure
ICF	Informed Consent Form
ICH	International Conference on Harmonization
IEC	Independent Ethics Committee
iFGF-23	c-Terminal Fibroblast Growth Factor-23
IMP	Investigational Medicinal Product
ITT	Intent to Treat
IRB	Institutional Review Board
IV	Intravenous
LDH	Lactate dehydrogenase
LLN	Lower Level of Normal
MAD	Multiple Ascending Dose
MCH	Mean corpuscular hemoglobin
MCHC	Mean corpuscular hemoglobin concentration
MCV	Mean corpuscular volume
MedDRA	Medical dictionary for regulatory activities
MSD	Meso Scale Discovery
NSAID	Non-Steroidal Anti-inflammatory Drug
PEA	Phosphoethanolamine
PINP	procollagen type I N-propeptide
PD	Pharmacodynamic
PK	Pharmacokinetic(s)
PKS	PK analysis sample
PLP	Pyridoxal 5'-phosphate
PopPK	Population PK

PPi	Inorganic Pyrophosphate
PT	Preferred Term
PTH	Parathyroid Hormone
ULN	Upper Level of Normal
SA-AKI	Sepsis Associated Acute Kidney Injury
SAE	Serious adverse event
SAD	Single Ascending Dose
SAS	Population for Safety Analysis
SD	Standard Deviation
SEM	Standard Error of the Mean
SOC	System Organ Class
TmP/GFR	ratio of tubular maximum reabsorption of phosphate (TmP) to glomerular filtration rate (GFR)
TRP	tubular reabsorption of phosphate
USP	United States Pharmacopeia
VD	Volume of distribution

1. INTRODUCTION

Recombinant human alkaline phosphatase (ilofotase alfa) is a full-length human chimeric alkaline phosphatase (ALP) that could benefit patients with hypophosphatasia (HPP), which is characterized by low activity of tissue-nonspecific isoenzyme of alkaline phosphatase (TNSALP).

1.1 Background

1.1.1 Alkaline Phosphatase and Hypophosphatasia

Hypophosphatasia is a rare, inherited, metabolic disease characterized by low activity of the tissue-nonspecific isoenzyme of alkaline phosphatase (TNSALP) biochemically characterized by an excess of extracellular inorganic pyrophosphate (PPi) and pyridoxal 5'-phosphate (PLP)². Treatment of HPP with a recombinant TNSALP (asfotase alfa) has demonstrated to be very effective in the infantile form³⁻⁶ and is currently in clinical investigation for the treatment of adults with juvenile onset HPP^{1,7}.

1.1.2 Recombinant Human Alkaline Phosphatase (ilofotase alfa)

Ilofotase alfa is a full-length human chimeric ALP derived by recombinant technology and produced in Chinese hamster ovary cells. Ilofotase alfa is encoded by a human intestinal ALP sequence wherein the sequence encoding the crown domain has been substituted with the corresponding human placental ALP sequence. The glycosylphosphatidylinositol (GPI) anchor has been removed resulting in a form that can be secreted. Ilofotase alfa has a projected mass of approximately 105 kDa based on the amino acid sequence derived from the deoxyribonucleic acid (DNA) sequence and approximately 130 kDa as a fully glycosylated molecule.

1.1.3 Clinical Studies with Recombinant Human Alkaline Phosphatase (ilofotase alfa)

In a Phase 1 single ascending dose (SAD) and multiple ascending dose (MAD) clinical trial in 51 healthy volunteers, all reported adverse events (AEs) were classified as mild or moderate and most were evenly distributed over the active and the placebo groups. The trial did not raise any safety concerns and single intravenous (iv) infusion of ilofotase alfa in the range of 0.32 mg/kg to 3.2 mg/kg (200 to 2000 U/kg), as well as daily iv infusions of ilofotase alfa at doses of 0.8 and 1.6 mg/kg (500 and 1000 U/kg) for three consecutive days, were well tolerated by healthy male and female patients.

A Phase 2a/2b Proof-of-Concept and Dose-Finding trial (STOP-AKI) with ilofotase alfa in 301 patients with SA-AKI (Sepsis Associated Acute Kidney Injury) has been completed. In Part 1 of STOP-AKI, patients were randomized to receive 0.4, 0.8, or 1.6 mg/kg of ilofotase alfa or placebo once a day for three consecutive days to identify the optimal dose. At the interim analysis, 1.6 mg/kg ilofotase alfa was selected by the Data Monitoring Committee (DMC) as the optimal ilofotase alfa dose for Part 2. In Part 2, 1.6 mg/kg ilofotase alfa was compared to placebo. The primary endpoint, the mean daily endogenous creatinine clearance (ECC) on Days 1 – 7 (area under the curve [AUC] 1-7 ECC), was not significant. However, ilofotase alfa showed a significant relative reduction in 28-day mortality of more than 40%. A positive effect on mortality was also seen in the 0.8 mg/kg dose. Overall, ilofotase alfa showed a long-term effect on the kidney function with significant improvement of ECC on day 21 and day 28 compared to day 1 and over the 28-day period. Non-fatal serious adverse events (SAEs) were comparable in the ilofotase alfa and placebo groups, indicating that the drug is well tolerated and safe.

A randomized, double-blind, placebo-controlled, two-arm parallel group, multi-center Phase 3 pivotal trial to investigate the efficacy and safety of ilofotase alfa for the treatment of patients with SA-AKI has recently been prematurely terminated (NCT04411472), in this trial no safety concerns were raised by the DMC.

A more detailed description of ilofotase alfa and results from non-clinical studies are provided in the Investigator Brochure (IB).

1.2 Rationale

Ilofotase alfa is a human recombinant enzyme replacement therapy that is hypothesized to be able to supplement deficient TNSALP and has demonstrated efficacy in animal models of HPP⁸. Ilofotase alfa has demonstrated to be effective and without safety concerns in adults with sepsis and acute kidney injury^{9,10}. This is a pilot trial for a potential Phase 2/3 trial aimed at identifying whether treatment with ilofotase alfa can normalize circulating levels of PPi, PLP and other biochemical markers of TNSALP deficiency along with the safety/tolerability of different doses of ilofotase alfa.

1.2.1 Risk – Benefit

No specific benefit to the participants in this trial can be expected, however the study results are intended to improve the understanding of ilofotase alfa and its potential as a possible additional future treatment option.

Ilofotase alfa has been assessed in healthy volunteers and in adults with sepsis and acute kidney injury, without serious safety or tolerability observations. In addition, the risks to subjects in this study will be minimized by an adequate selection of the eligibility criteria and diligent close medical monitoring, including both clinical symptoms as laboratory assessments and wider parameters of the subjects.

Overall, risks are considered justified by the benefit of a potential additional future treatment option in HPP.

2. OBJECTIVES

Primary objective:

- The change in Inorganic Pyrophosphate (PPi) and Pyridoxal 5'-phosphate (PLP) levels after low and high dose of ilofotase alfa in adult HPP patients.

Exploratory objective:

- To determine the safety and pharmacokinetic (PK) profile of a single intravenous dose of ilofotase alfa in adult HPP patients.
- To determine the pharmacodynamic (PD) profile of a single intravenous dose of ilofotase alfa in adult HPP patients.

3. INVESTIGATIONAL PLAN

3.1 Trial Design and Plan

3.1.1 Trial design

This is a single-center, open-label, randomized, parallel group clinical trial in adult patients with HPP. Two different dose levels (0.8 mg/kg and 3.2 mg/kg) will be assessed. Up to twelve (12) patients will be randomized to one of two trial arms, 6 in each trial arm.

Patients will receive a single dose of 0.8 mg/kg or a single dose of 3.2 mg/kg. Ilofotase alfa will be administered as a 1-hour intravenous infusion on day 1.

3.1.2 Screening and Informed consent

Patients will report for the eligibility screening according to the inclusion and exclusion criteria defined in Section 3.2 within 6 weeks prior to the first drug administration.

Patients will voluntarily sign the trial specific Informed Consent Form (ICF) prior to any trial specific screening procedures being performed. The written informed consent will be obtained for all patients, regardless of their eligibility for the trial; the signed ICFs will be retained and archived at the trial center and another copy will be provided to the patient.

Eligibility screening will consist of assessments as presented in the Schedule of assessments Table 1.

3.1.3 Treatment Period

The patients will arrive at the clinical research center two days (day -2) before the drug administration (day 1 is the day of drug administration). Patients will leave the research center at the end of the observation period on day 10 after completion of all assessments (see Schedule of Assessments Table 1). Assessments will be performed during the treatment period as presented in the Schedule of Assessments (see Table 1).

3.1.4 Follow-up

The follow-up will be performed at day 15. The specific procedures that will be performed are presented in the Schedule of Assessments (see Table 1).

3.1.5 Discussion Trial Design

A randomized, open-label design was chosen to assist the medical assessment of whether there is a change in PPi, and PLP between the two different doses. HPP patients may have a history of elevated

serum levels in either PPi or PLP, or both. The doses selected, single doses of 0.8 mg and 3.2 mg, were also assessed in the single ascending dose studies in healthy volunteers AP-recAP-AKI-01-01 and AP-recAP-AKI-01-02 previously conducted. This dosing regimen has been administered to both healthy volunteers and SA-AKI patients without relevant safety observations. Since both doses administered in the current trial have been administered previously in other clinical trials, the groups can be dosed in parallel.

3.2 Selection of Trial Population

Up to 12 patients should be enrolled.

3.2.1 Inclusion Criteria

At screening, the following inclusion criteria must be met:

1. 18-85 years old, inclusive, at screening.
2. Genetically confirmed variant in the ALPL-Gene.
3. Clinical symptoms of HPP.
4. Medical history with 1) at least two independent measures of Alkaline Phosphatase (ALP) below lower level of normal (LLN) and 2) at least one measurement of PPi or PLP above upper level of normal (ULN).
5. Provision of signed and dated informed consent form (ICF) in accordance with local regulations at baseline.
6. Patients must agree not to get pregnant/not to get their partner pregnant, during the trial
 - Women of Child Bearing Potential must agree to use adequate and effective contraception means (criteria CTFG, 2020¹¹) for the period between trial drug administration and 14 days thereafter.
 - Post-menopausal females not requiring hormonal contraception are defined as: no menses for 12 months without an alternative cause, and follicle stimulating hormone level must be used to confirm post-menopausal state in women not using hormonal contraception or hormonal replacement therapy (CTFG, 2020).
 - Male subjects must agree to wear a condom during sexual intercourse and in case their partner is of child bearing potential they must agree to use adequate and effective contraception means (criteria CTFG, 2020) for the period between trial drug administration and 14 days thereafter.

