30. MRZ. 2023

PROTOCOL SYNOPSIS

Open-Label Pilot Trial to Evaluate the Effects of Ilofotase Alfa on Biomarkers in Adult Patients with Hypophosphatasia

Title (short)

Pilot trial of single dose ilofotase alfa in hypophosphatasia

Trial code

Sponsor code: AP-recAP-HPP-01-01

Sponsor

AM-Pharma BV
[name]
The Netherlands

Trial center

Clinical Osteology and Clinical Trial Unit
Konig Ludwig Haus
[name]
[name]
Germany

Objectives

Primary objective:

- The change in Inorganic Pyrophosphate (PPi), and Pyridoxal 5'-phosphate (PLP) levels after low, and high dose ilofotase alfa in adult hypophosphatasia (HPP) patients.

Exploratory objectives:

- To determine the safety and pharmacokinetic (PK) profile of a single iv dose of ilofotase alfa in adult HPP patients.
- To determine the pharmacodynamic (PD) profile of a single iv dose of ilofotase alfa in adult HPP patients.

Design and Treatments

This is a single-center, open-label, randomized, parallel group clinical trial in adult patients with HPP. Two different dose levels (0.8 mg/kg and 3.2 mg/kg) will be assessed. Up to twelve patients will be randomized, 6 patients to each trial arm. Patients will receive a single dose of 0.8 mg/kg or a single dose of 3.2 mg/kg. Ilofotase alfa will be administered as a 1-hour iv infusion on day 1.

Trial period

The trial period will include a run-in period of 2 days (day -2 to day -1) before administration of ilofotase alfa (day 1), followed by 9 days of observation after the ilofotase alfa administration (day 2 to day 10), with an additional follow-up assessment 14 days after ilofotase alfa administration (day 15).

Patients

Up to twelve (12) patients \geq 18 years and \leq 85 years of age with HPP.

Inclusion criteria

At screening, the following inclusion criteria must be met:

1. 18-85 years old, inclusive.
2. Genetically confirmed variant in the tissue-nonspecific isozyme alkaline phosphatase (ALPL)-Gene.
3. Clinical symptoms of HPP.
4. Medical history with 1) at least two independent measures of Alkaline Phosphatase (ALP) below lower level of normal (LLN) and 2) at least one measurement of either PPi or PLP above upper level of normal (ULN).
5. Provision of signed and dated informed consent form (ICF) in accordance with local regulations at screening.
6. Patients must agree not to get pregnant/not to get their partner pregnant, during the trial:

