3.3.13 Prohibited Medication During the Trial (including the screening period)

1. NSAIDs
2. Corticosteroids
3. Compounds intended to interfere with bone metabolism (e.g. Denosumab, Teriparatide, Romosozumab, Raloxifene).
4. Bisphosphonates
5. Supplements including Vitamin B6
6. Asfotase alfa

If there is a clinical indication to start any of these above medication, the subject should be withdrawn from the trial. Subjects who initiate any of the medication mention above during the trial period will be considered dropouts.

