3.3.14 Female subjects

Women of Child Bearing Potential (i.e. fertile, following menarche and until becoming post-menopausal unless permanently sterile) must have adequate and effective contraception means. Methods that are considered as highly effective birth control methods are: 1) Combined (estrogen and progestogen containing) hormonal contraception associated with inhibition of ovulation (oral, intravaginal or transdermal), 2) progestogen-only hormonal contraception associated with inhibition of ovulation (oral, injectable, implantable), 3) intrauterine device (IUD), 4) intrauterine hormone-releasing system (IUS), 5) bilateral tubal occlusion, 6) vasectomised partner, 7) sexual abstinence. Contraception methods 3, 4, 5 and 6 have lower user dependency and should preferably be used, in particular when contraception is introduced as a result of participation in the clinical trial. (CTFG, 2020¹¹)

For post-menopausal female, with post-menopause defined as no menses for 12 months without an alternative medical cause, a high follicle stimulating hormone (FSH) level in the postmenopausal range may be used to confirm a post-menopausal state in women not using hormonal contraception or hormonal

replacement therapy. However, in the absence of 12 months of amenorrhea, a single FSH measurement is insufficient. (CTFG, 2020¹¹)

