- It is **not** acceptable for the Investigator to send photocopies of the patient's medical records to the Sponsor or its designee in lieu of completion of the AE/SAE documentation.
- There may be instances when copies of medical records for certain cases are requested by the Sponsor or its designee. In this case, all patient identifiers, except for the patient number, will be blinded on the copies of the medical records before submission to the Sponsor or its designee.
- The Investigator will attempt to establish a diagnosis of the event based on signs, symptoms, and/or other clinical information. In such cases, the diagnosis (not the individual signs/symptoms or related procedure), as well as indication for the procedure, will be documented as the AE/SAE.

- All AEs must be reported in detail on the appropriate page of the eCRF.
- Follow-up of AEs will continue until resolution, stabilization, or death. In case of ongoing aEs at the moment of database closure, the data obtained at the moment of database closure will be used in the statistical analysis. The follow-up of the AE will be documented in the source documents and will be described in the final report only if considered relevant by the Principal Investigator.
- SAEs will be collected from Screening until the final trial visit. SAEs that are related to the investigational drug and continue beyond the normal collection period (i.e., are ongoing at the time a patient exits the trial) will be followed until resolution or until stabilized with sequelae. SAEs that begin after the patient's participation in the trial is complete, but that the Principal Investigator considers to be related to trial medication, may be reported at any time.
- The Principal Investigator or clinical site personnel should notify the Sponsor via email ([contact]) or [contact]) regardless of relationship to the investigational drug, within 24 hours of clinical site personnel becoming aware of the event. The Principal Investigator will provide the initial notification by forwarding a completed "SAE Notification Form" or the relevant, which must include the Principal Investigator's assessment of the relationship of the event to investigational drug.
- New or updated information will be recorded in the originally completed eCRF.
- The Investigator will submit any updated SAE data to the Sponsor or its designee within 24 hours of receipt of the information.

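### The dated contraception period for women of child-bearing potential opens only at dosing; it should open at screening/consent (minor)

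*Protocol*

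**What the plan says.** Criterion 6 (3.2.1, repeated in the synopsis) opens with a general promise: "Patients must agree not to get pregnant/not to get their partner pregnant, during the trial". The bullet for women then sets the specific duty, "Women of Child Bearing Potential must agree to use adequate and effective contraception means", and gives its dates: "for the period between trial drug administration and 14 days thereafter". The bullet for men has the same dates.

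Other places bear on when the duty begins:

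- Section 3.3.14 states that women of child-bearing potential "must have adequate and effective contraception means". It gives neither a start nor an end.
- Section 3.1.2 places eligibility screening "within 6 weeks prior to the first drug administration". Table 1 has no separate screening column; consent, the eligibility check and the first pregnancy test stand under day -2.
- Table 1 schedules pregnancy tests on day -2, day 1 and day 15. Exclusion 11 bars a woman who is pregnant at screening or baseline.
- Section 3.1.3 has patients at the center from day -2 to day 10.
- On what counts as the trial, the synopsis (Trial period) says "The trial period will include a run-in period of 2 days (day -2 to day -1"), followed by dosing and observation. The heading of 3.3.13 reads "Prohibited Medication During the Trial (including the screening period"), and Appendix 7.1 says "SAEs will be collected from Screening until the final trial visit".

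**The concern.** The whole exposure is one infusion on day 1, and it cannot be undone. To keep an early pregnancy from being exposed, contraception has to be working in the days before the infusion. The only dated rule starts at the infusion itself. The day 15 test and the pregnancy follow-up in 3.5.2.7 act only afterwards.

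The two pre-dose tests detect an established pregnancy, but a very recent conception can be negative on both. The days that matter are therefore the outpatient days just before admission, and no dated rule reaches them. What is at stake is participant safety in a trial whose risk-benefit section (1.2.1) expects no specific benefit for participants and relies partly on the eligibility criteria to limit risk.

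**Working it through.** The protocol gives no figure to reproduce. The check compares the texts and counts calendar days.

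**Inputs.** The dated rule starts at dosing and ends 14 days later (3.2.1, synopsis). Screening is at most 6 weeks before dosing, 6 × 7 = 42 days (3.1.2), and can be as late as day -2 (Table 1). Admission is on day -2 (3.1.3). There is no day 0 (Table 1 footnote), so day -2 is 2 days before day 1.

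**Where the dated window falls.** Day 1 to day 15 is 15 - 1 = 14 days. Of these, 10 - 1 = 9 run from dosing to discharge on day 10, with the woman at the center, and 15 - 10 = 5 follow discharge. None is before dosing.

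**Pre-dose days covered under each reading.** Outpatient days are pre-dose days minus the 2 at the center.

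| Reading | Pre-dose days | Of these, outpatient |
|---|---|---|
| Dated rule alone | 0 | 0 |
| Trial begins on day -2 (synopsis) | 2 | 2 - 2 = 0 |
| Trial includes screening (as in 3.3.13 and Appendix 7.1), or 3.3.14 is a condition met at screening | 2 to 42 | 0 to 42 - 2 = 40 |

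The protocol's own texts therefore allow anything from 0 to 40 outpatient days of cover. The answer depends on which sentence is followed and on when screening happens.

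**Illustration of the lead time.** The protocol gives neither the type nor the sensitivity of the pregnancy test. Assume that a test can still be negative up to L days after conception, with L between 7 and 14. Conceptions 3 to L days before dosing are then outpatient and pass both tests, which is L - 2 days: 7 - 2 = 5, or 14 - 2 = 12. If the duty starts at screening, S days before dosing, the days left uncovered are L - S, and never less than 0:

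- S = 14 or more: 0 days for both values of L.
- S = 7: 7 - 7 = 0 days (L = 7), or 14 - 7 = 7 days (L = 14).
- S = 2 (screening on day -2): 5 or 12 days.

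A start at screening thus closes the illustrated gap whenever screening is at least 14 days before dosing. It cannot do so by itself when consent is given on day -2.

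**The case against.** The strongest reply is that the protocol already asks for contraception before dosing. Section 3.3.14 is unconditional and is not limited to the days after dosing. Several of the methods it prefers, such as an intrauterine device or a vasectomised partner, would be in place before the dosing day. The inclusion criteria have to be met at screening. Where the protocol elsewhere spells out what the trial covers (3.3.13), it includes screening, and the synopsis text on the trial period describes visits more than it defines when duties begin. Exclusion 11, two tests and the stay from day -2 do the rest. Any remaining outpatient days before a day -2 consent are days before consent, when no participant duty can bind.

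Much of this stands. A reader might infer that women may go without contraception until the infusion, or that up to 6 weeks are left unprotected. The documents do not support that: 3.3.14 and the lead sentence of criterion 6 point the other way, and the tests would pick up all but a very recent conception. A reader might also take 5 to 12 days as the size of a gap in the protocol. It is not, because it depends on an assumed test lag and ignores 3.3.14 read as an entry condition.

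What the reply does not remove is that the one sentence carrying dates gives the wrong start for its purpose, and that no other sentence supplies a start. Section 3.3.14 also foresees contraception being started because of participation, so it cannot be taken to show that contraception was already in use. The wording of 3.3.13 shows that the protocol can name the screening period when it means to; criterion 6 does not.

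**Conclusion.** The point holds as a minor defect of a stated rule. The dated contraception period for women of child-bearing potential begins later than its purpose requires, and the two softer texts suggest an earlier start without fixing one.

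The residual risk is small: up to 12 patients, one infusion, pregnancy tests on day -2 and day 1, and the stay at the center from day -2. It cannot be quantified from the protocol, which gives neither the number of such women nor the test's sensitivity. That a very early conception can test negative is general biology, not a statement in the protocol, and the 7 to 14 day lag is an assumption used only for illustration.

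No claim is made that the drug harms a pregnancy, or about what the Investigator Brochure, the cited contraception guidance or the consent form may add; none of these is at hand. Endpoints, analysis sets and estimates are unaffected.

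**What to change.** For women of child-bearing potential, change the period in criterion 6 (3.2.1 and synopsis) so that it runs from screening/consent until 14 days after dosing, and put the same period into 3.3.14. Leave the male window as written: a man has received no drug before dosing.

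The cost is wording in the protocol and the consent form, and a slightly longer contraception duty.

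As an option for the sponsor, where screening falls close to dosing, contraception or abstinence could be required to have been in place for about 14 days before dosing or since the last menses. That would cover the late-screening case, but it is a new eligibility condition open to debate. For a woman not yet using contraception it could mean earlier consent, which 3.1.2 already allows, or a short delay. If adopted, it should be checked before day -2 is booked, so that run-in samples and the pregnancy test need not be repeated.
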